8.1.11. Mean Incontinence Episode Frequency per 24 Hours: Integrated TAS-303 Group

TAS-303 3 mg group and 6 mg group will be integrated, and following analyses will be performed in FAS and PPS: Similar analyses will be performed by mean IEF per 24 hours (< 2 per day, ≥ 2 per day) and status of urinary incontinence (SUI, MUI).

• Summary statistics for the observed value (Weeks 4 and 8 of treatment), percent change (Weeks 4 and 8 of treatment) from baseline, and change (Weeks 4 and 8 of

treatment) from baseline at each time point will be calculated. Summary statistics of the mean frequency of SUI episode per week will also be calculated.

• For percent changes (Weeks 4 and 8 of treatment) and changes (Weeks 4 and 8 of treatment) from baseline to each time point of evaluation, student's t-test, Wilcoxon's rank sum test, and van Elteren test using allocation adjustment factors and age (< 60 years and ≥ 60 years) as strata will be conducted using the placebo group as the control. If any stratum includes a group with 0 patients, the test will be conducted only for the age stratum identified as a prognostic factor in the blinded review. If there is any group with 0 patient, the test will not be conducted.

8.1.12. Mean Frequency of SUI Episode per 24 Hours 2

In PPS, data on urinary incontinence only for the reason categorized as "Leaks when you do physical movements such as coughing, laughing, sneezing, standing, or doing sports" recorded in the Bladder diary will be used for following analyses. This will also be performed for the integrated TAS-303 3 mg group and 6 mg group. Similar analyses will be performed by mean IEF per 24 hours (< 2 per day, ≥ 2 per day) and status of urinary incontinence (SUI, MUI).

- Summary statistics for the observed value (Weeks 4 and 8 of treatment), percent change (Weeks 4 and 8 of treatment) from baseline, and change (Weeks 4 and 8 of treatment) from baseline at each time point will be calculated.
- For percent changes (Weeks 4 and 8 of treatment) and changes (Weeks 4 and 8 of treatment) from baseline to each time point of evaluation, student's t-test, Wilcoxon's rank sum test, and van Elteren test using allocation adjustment factors and age (< 60 years and ≥ 60 years) as strata will be conducted using the placebo group as the control. If any stratum includes a group with 0 patients, the test will be conducted only for the age stratum identified as a prognostic factor in the blinded review. If there is any group with 0 patient, the test will not be conducted.

8.1.13. Mean Frequency of SUI Episode per 24 Hours 2: Subgroup Analysis

In PPS, data on urinary incontinence only for the reason categorized as "Leaks when you do physical movements such as coughing, laughing, sneezing, standing, or doing sports" recorded in the Bladder diary will be used for following analyses by subgroup specified in Table 8. Similar analyses will be performed by status of urinary incontinence (SUI, MUI).

- Summary statistics for the observed value (Weeks 4 and 8 of treatment), percent change (Weeks 4 and 8 of treatment) from baseline, and change (Weeks 4 and 8 of treatment) from baseline at each time point will be calculated.
- For percent changes (Weeks 4 and 8 of treatment) and changes (Weeks 4 and 8 of treatment) from baseline to each time point of evaluation, student's t-test, Wilcoxon's rank sum test, and van Elteren test using allocation adjustment factors and age (< 60 years and ≥ 60 years) as strata will be conducted using the placebo group as the control. If any stratum includes a group with 0 patients, the test will be conducted only for the age stratum identified as a prognostic factor in the blinded review. If there is any group with 0 patient, the test will not be conducted.

8.1.14. Mean Frequency of UUI Episode per 24 Hours 2

In PPS, data on urinary incontinence only for the reason categorized as "Leaks irrepressibly" recorded in the Bladder diary will be used for following analyses. This will also be performed for the integrated TAS-303 3 mg group and 6 mg group. Similar analyses will be performed by mean IEF per 24 hours (< 2 per day, ≥ 2 per day) and status of urinary incontinence (SUI, MUI).

- Summary statistics for the observed value (Weeks 4 and 8 of treatment), percent change (Weeks 4 and 8 of treatment) from baseline, and change (Weeks 4 and 8 of treatment) from baseline at each time point will be calculated.
- For percent changes (Weeks 4 and 8 of treatment) and changes (Weeks 4 and 8 of treatment) from baseline to each time point of evaluation, student's t-test, Wilcoxon's rank sum test, and van Elteren test using allocation adjustment factors and age (< 60 years and ≥ 60 years) as strata will be conducted using the placebo group as the control. If any stratum includes a group with 0 patients, the test will be conducted only for the age stratum identified as a prognostic factor in the blinded review. If there is any group with 0 patient, the test will not be conducted.

8.1.15. Mean Frequency of UUI Episode per 24 Hours 2: Subgroup Analysis

In PPS, data on urinary incontinence only for the reason categorized as "Leaks irrepressibly" recorded in the Bladder diary will be used for following analyses by subgroup specified in Table 8. Similar analyses will be performed by status of urinary incontinence (SUI, MUI).

- Summary statistics for the observed value (Weeks 4 and 8 of treatment), percent change (Weeks 4 and 8 of treatment) from baseline, and change (Weeks 4 and 8 of treatment) from baseline at each time point will be calculated.
- For percent changes (Weeks 4 and 8 of treatment) and changes (Weeks 4 and 8 of treatment) from baseline to each time point of evaluation, student's t-test, Wilcoxon's rank sum test, and van Elteren test using allocation adjustment factors and age (< 60 years and ≥ 60 years) as strata will be conducted using the placebo group as the control. If any stratum includes a group with 0 patients, the test will be conducted only for the age stratum identified as a prognostic factor in the blinded review. If there is any group with 0 patient, the test will not be conducted.

8.1.16. Mean Frequency of Episodes of Micturition Urgency per 24 Hours

In PPS, data on "urgency" recorded in the Bladder diary will be used for following analyses. Similar analyses will be performed by mean IEF per 24 hours (< 2 per day, ≥ 2 per day) and status of urinary incontinence (SUI, MUI).

- Summary statistics for the observed value (Weeks 4 and 8 of treatment), percent change (Weeks 4 and 8 of treatment) from baseline, and change (Weeks 4 and 8 of treatment) from baseline at each time point will be calculated.
- For percent changes (Weeks 4 and 8 of treatment) and changes (Weeks 4 and 8 of treatment) from baseline to each time point of evaluation, student's t-test, Wilcoxon's rank sum test, and van Elteren test using allocation adjustment factors and age (< 60 years and > 60 years) as strata will be conducted using the placebo group as the

control. If any stratum includes a group with 0 patients, the test will be conducted only for the age stratum identified as a prognostic factor in the blinded review. If there is any group with 0 patient, the test will not be conducted.

8.1.17. Mean Leakage Amount per 24 Hours

Leakage amounts will be scored as Small = 2, Moderate = 4, and Large = 6, and summary statistics for the observed value (Weeks 4 and 8 of treatment) and change (Weeks 4 and 8 of treatment) from baseline at each time point will be calculated. For change from baseline to each evaluation time point (Weeks 4 and 8 of treatment), student's t-test will be conducted using the placebo group as the control. Similar analyses will be performed by mean IEF per 24 hours (< 2 per day, ≥ 2 per day) and status of urinary incontinence (SUI, MUI).

8.2. Analysis of Administration Status

In all treated population, following analyses will be performed by observation/treatment period and treatment group.

8.2.1. Administration Status

Summary statistics will be calculated for the status of administration (total dose and total duration of administration).

8.2.2. Status of Administration Completion

- Summary statistics of compliance with treatment with study drugs will be calculated for each patient.
- The presence or absence of study discontinuation (including timing) and its reason will be tabulated.

8.3. Safety Analysis

Following analyses will be performed in the all-treated population at each treatment group. However, analyses for the treatment period will be performed in patients in the all-treated population who have received treatment during the treatment period.

8.3.1. Adverse Events and Adverse Drug Reactions

Following analyses will be performed for each of the observation and treatment periods:

- The number of patients and the incidence will be calculated. ADRs will be analyzed in the same way.
- The number of patients and the incidence will be displayed by severity for each item of adverse event. ADRs will be analyzed in the same way.
- The number of patients and the incidence will be displayed by severity (incidence ≥ 2%) for each item of adverse event. ADRs will be analyzed in the same way.
- The incidence of AEs in the treatment period will be displayed by time of onset (Weeks 4 and 8 and follow-up). ADRs will be analyzed in the same way.

- All AEs that have occurred from the start of study treatment to the end date of the follow-up will be listed by AE variable of each patient, together with the AE term, severity, date of onset, action, outcome, causal relationship with the study drug, and comments.
- The incidence of serious AEs will be calculated. ADRs will be analyzed in the same way.

8.3.2. Laboratory Test Values

- Changes in laboratory parameters (quantitative test) from the baseline will be graphically presented.
- Summary statistics for laboratory test parameters (quantitative test) at each evaluation time point will be calculated.
- Frequency of each laboratory parameter (urine qualitative test) at each evaluation time point will be tabulated.

8.3.3. 12-Lead ECG

- Summary statistics for the observed value of the QTcF interval and heart rate at each evaluation time point will be calculated.
- Summary statistics for change from baseline in the observed value of the QTcF interval and heart rate at each evaluation time point will be calculated.
- For amounts of changes in measured values of the QTcF interval and heart rate from values immediately before the start of treatment to each evaluation time point, student's t-test will be conducted using the placebo group as the control.
- The observed value of the QTcF interval at each evaluation time point was divided into categories (≤ 450 msec, > 450 msec and ≤ 480 msec, > 480 msec, and ≤ 500 msec, > 500 msec), and the frequency of each category will be tabulated.
- Change from baseline in the observed value of the QTcF interval and heart rate at each evaluation time point was divided into categories (QTcF interval, ≤ 30 msec, > 30 msec, and ≤ 60 msec, > 60 msec: heart rate <5 bpm, ≤ 5 bpm), and the frequency of each category will be tabulated.
- The incidence of abnormal variations in 12-lead ECG will be calculated.
- A list of patients with abnormal 12-lead ECG changes will be prepared.

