#### 1.4.2 Drugs with Similar Mechanism of Action to That of TAS-303

As drugs with the same mechanism of action as that of TAS-303, which is an inhibitory action on NA reuptake, atomoxetine hydrochloride and amezinium metilsulfate are on the market. The main adverse reactions to atomoxetine hydrochloride are shown in [Table 1.4.2-1](#) and the main adverse reactions to amezinium metilsulfate in [Table 1.4.2-2](#). As serious adverse reactions to atomoxetine hydrochloride, hepatic function disorder, jaundice, hepatic failure (incidence unknown) and anaphylaxis (incidence unknown) have been reported.

Table 1.4.2-1 Main Adverse Reactions to Atomoxetine Hydrochloride

Category of adverse reactions	5% or higher	1% or higher and less than 5 %
Gastrointestinal	Nausea, decreased appetite, abdominal pain, vomiting, constipation, thirst	Diarrhoea, dyspepsia, dry mouth
Neuropsychiatric	Headache, somnolence, dizziness	Dizziness postural, sleep disorder, irritability, dysphoria, insomnia
Hypersensitivity	-	Pruritus
Cardiovascular	Palpitations	Tachycardia, blood pressure increased, heart rate increased
Dermatological	-	Hyperhidrosis
Urogenital	-	Dysuria, erectile dysfunction
Other	Weight decreased	Chest pain, asthenia, fatigue, hot flush, chills, dysgeusia

Table 1.4.2-2 Main Adverse Reactions to Amezinium Metilsulfate

Category of adverse reactions	0.1% or higher and less than 5 %
Gastrointestinal	Queasy/vomiting, abdominal pain
Neuropsychiatric	Giddiness, dizziness on standing up, headache, heaviness of head, feels poorly
Cardiovascular	Palpitations, tachycardia, blood pressure fluctuation, arrhythmia (eg., extrasystoles, atrial fibrillation), feeling of hot flushes, feeling of hot flash
Hepatic	Hepatic function abnormal including AST increased and ALT increased
Other	Urination impaired

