#### **(2) Adverse reactions**

- Analyses similar to those for adverse events are performed for adverse reactions

(except preparation of the list).

(3) Blood pressure, pulse rate and body temperature

- Summary statistics of blood pressure, pulse rate and body temperature are calculated for each evaluation time point.
- Summary statistics of the amount of change in measured values of blood pressure and pulse rate from the values immediately before the start of the treatment with the study drugs are calculated for each evaluation time point.
- For blood pressure and pulse rate, the amount of change in measured values at each evaluation time point from the values immediately before the start of the treatment with the study drugs is categorized and the frequency for each category is calculated.

(4) 12-lead Electrocardiography

A test item based on 12-lead electrocardiogram, QT interval corrected using Fridericia's formula (QTcF) is used.

- Summary statistics of measured values of QTcF and heart rate are calculated for each evaluation time point.
- Summary statistics of the amount of change in measured values of QTcF and heart rate from the values immediately before the start of the treatment with the study drugs are calculated for each evaluation time point.
- For QTcF, measured values at each evaluation time point are categorized and the frequency for each category is calculated.
- For QTcF and heart rate, the amount of change in measured values at each evaluation time point from the values immediately before the start of the treatment with the study drugs is categorized and the frequency for each category is calculated.
- Subjects with abnormal changes in 12-lead electrocardiogram are listed.

(5) Laboratory test values

- Summary statistics of each laboratory test item are calculated for each evaluation time point.

(6) Urinary flow test

- Summary statistics of each item of urinary flow test (maximum urinary flow rate [free  $Q_{max}$ ], average urinary flow rate [free  $Q_{ave}$ ], voided volume and time of voiding) are calculated for each evaluation time point.
- Summary statistics of the amount of change in measured values of each urinary flow test item from the values immediately before the start of the treatment with the study drugs are calculated for each evaluation time point.

(7) Residual urine volume

- Summary statistics are calculated for each evaluation time point.

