8.3.4. Blood Pressure, Pulse Rate, and Body Temperature

- Summary statistics for blood pressure, pulse rate, and body temperature at each evaluation time point will be calculated.
- Summary statistics for change from baseline in the observed value of blood pressure and pulse rate at each evaluation time point will be calculated.

- For amounts of changes in measured values of blood pressure and pulse rate from values immediately before the start of treatment to each evaluation time point, student's t-test will be conducted using the placebo group as the control.
- Change from baseline in the observed value of blood pressure and pulse rate at each evaluation time point will be divided into categories (blood pressure, < 10 mmHg, ≥ 10 mmHg: pulse rate, < 5 bpm, ≥ 5 bpm), and the frequency of each category will be tabulated.

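### SAP 8.3.3 prints nested categories for change in ECG heart rate, so one descriptive safety table has no row for a rise above 5 bpm

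*SAP*

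**What the plan says.** The protocol asks for this table. Item (4), 12-lead Electrocardiography, of its safety analysis says: "For QTcF and heart rate, the amount of change in measured values at each evaluation time point from the values immediately before the start" of study drug is to be put into categories and the frequency of each calculated. It gives no cut-points.

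SAP 8.3.3 supplies them. It says: "Change from baseline in the observed value of the QTcF interval and heart rate at each evaluation time point was divided into categories". For heart rate the categories are "heart rate <5 bpm, ≤ 5 bpm". For QTcF, in the same bullet, they are "QTcF interval, ≤ 30 msec, > 30 msec, and ≤ 60 msec, > 60 msec".

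SAP 8.3.4 plans the matching table for pulse rate as a vital sign and defines its categories as "pulse rate, < 5 bpm, ≥ 5 bpm".

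Between the protocol and the SAP, the bullet in 8.3.3 is the only definition of the ECG heart-rate categories. SAP 12 says that the full set of analyses is laid out in a separate Table and Figure Plan, which is not among the documents.

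**The concern.** A frequency table needs categories that each patient enters exactly once. The two heart-rate categories in 8.3.3 differ only in whether a change of exactly 5 bpm is included. They overlap almost completely, and both stop at 5 bpm. A larger rise belongs to neither.

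A rise in heart rate is a foreseeable effect here. Protocol 1.4.2 describes two marketed drugs as sharing the inhibition of noradrenaline reuptake. For atomoxetine its table lists, at 1% or higher and less than 5%, "Tachycardia, blood pressure increased, heart rate increased", with palpitations at 5% or higher. For amezinium it lists palpitations and tachycardia. The missing row is therefore the one that a safety reader would look at first.

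The SAP change log records two additions to 8.3.3 in Version 3.0, so the section was reopened and this definition remained.

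**Working it through.** The plan states no figure on this point, so there is none to reproduce. The question is whether each printed set of categories holds every possible change exactly once.

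**Inputs.** Let d be the change from baseline.

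- ECG heart rate (SAP 8.3.3): A is d < 5, B is d ≤ 5.
- Pulse rate (SAP 8.3.4): d < 5, d ≥ 5.
- QTcF change (SAP 8.3.3): d ≤ 30, 30 < d ≤ 60, d > 60.

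**Step 1: count the categories that contain each whole-number change.** The ranges are illustrative: −40 to +40 bpm (81 values) and −100 to +100 msec (201 values). The pattern does not depend on them. The entries are possible values of d, not patients.

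| Categories | Values | In none | In exactly one | In two |
|---|---|---|---|---|
| ECG heart rate, as printed | 81 | 35 (+6 to +40) | 1 (+5) | 45 (−40 to +4) |
| Pulse rate, 8.3.4 | 81 | 0 | 81 | 0 |
| QTcF change, 8.3.3 | 201 | 0 | 201 | 0 |

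The heart-rate row adds up: 35 + 1 + 45 = 81. Only this set fails. The set beside it in the same bullet and the set in the next section both work.

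**Step 2: what the printed table would contain.** On the same grid, row A holds 45 values and row B holds 45 + 1 = 46. The rows sum to 45 + 46 = 91, although only 81 values exist. The excess of 10 is the 45 counted twice less the 35 not counted. In a real table the percentages would therefore not, in general, add to 100%.

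**Step 3: what can be recovered.** Let N be the number assessed, n(A) the count below 5 and n(B) the count at or below 5.

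- Above 5 bpm: N − n(B). On the grid, 81 − 46 = 35.
- Exactly 5 bpm: n(B) − n(A). On the grid, 46 − 45 = 1.
- At or above 5 bpm: N − n(A). On the grid, 81 − 45 = 36.

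N is available, because SAP 6.2.2.1 requires the sample size with all summary statistics and 8.3.3 plans these for the same variable: "Summary statistics for change from baseline in the observed value of the QTcF interval and heart rate at each evaluation time point will be calculated".

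**Step 4: the same check with the sign reversed.** With <5 bpm and ≥5 bpm, each of the 81 values falls in exactly one category.

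**The case against.** The finding rests on one inequality sign in text that a program read from a PDF, and signs are not rendered evenly there. SAP 8.1.16 prints > 60 years where the same rule in 8.1.1, 8.1.7 and 8.1.8 has ≥ 60 years. A misread sign in 8.3.3 is possible, even though ≥ comes through correctly in 8.3.1 and 8.3.4. The Table and Figure Plan may also carry the right sign. Both points stand, and they are why the fix begins with a check. If only the Table and Figure Plan is right, the SAP still needs to agree with it.

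A reader might infer that patients with a rise above 5 bpm are lost or hidden. The documents do not support that. The count follows by subtraction (Step 3), so what is missing is a row, not data.

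A reader might also infer that a heart-rate effect could go unseen. That does not follow either. SAP 8.3.3 also plans summary statistics of the change (6.2.2.1 requires the quartiles and the maximum), a t-test against placebo, the incidence of abnormal ECG variations and a list of the patients concerned. SAP 8.3.4 plans a correctly split pulse-rate table with its own t-test. Protocol 5.1.5 and 5.1.8 require clinically significant changes in vital signs and ECG to be recorded as adverse events. What remains is narrower. None of these gives the protocol's own table, a count of patients by category of change in ECG heart rate: the summary statistics and t-test describe groups, and pulse rate is a separate measurement.

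Finally, it is tempting to put a percentage on the patients without a row. With a normal distribution of the change, an assumed mean of 0 and SD of 8 bpm gives about 27% above 5 bpm, and mean 0 with SD 10 gives about 31%. A mean of 5 gives 50%, but only because the mean is set at the cut-point. No such mean or SD is in either document, so these figures illustrate the assumptions and say nothing about this trial.

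**Conclusion.** The point holds as a minor correction. As printed, the heart-rate categories in SAP 8.3.3 are nested and have no place for a rise above 5 bpm. A literal program would produce a faulty version of a table that the protocol requires. The pulse-rate rule in 8.3.4 and the QTcF rule in the same bullet make a reversed sign the most likely explanation.

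The effect is confined to one descriptive safety table. No hypothesis test, estimate, analysis population or decision rule depends on it. The share of patients affected cannot be stated. The conclusion assumes that the sign in the source SAP is the one printed here. If the source already reads ≥, there is nothing to correct in the SAP.

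**What to change.** 1. Check the sign in 8.3.3 against the source SAP and against the Table and Figure Plan.
2. If it is as printed, change the heart-rate categories in 8.3.3 to <5 bpm and ≥5 bpm, to match 8.3.4, and record the change in the log as SAP 10 requires.
3. Verify the table shell, the program and any output already produced. The log places Version 2.0 before key-code breaking and describes Version 3.0 as adding further analyses, so tables may already exist. If one was run as printed, rerun it; N − n(A) gives the row for 5 bpm or more as a cross-check.

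The cost is one character in the SAP, a log entry and, at most, one rerun of a table. No data collection, endpoint, test or sample size changes.

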8.3.4. Blood Pressure, Pulse Rate, and Body Temperature

- Summary statistics for blood pressure, pulse rate, and body temperature at each evaluation time point will be calculated.
- Summary statistics for change from baseline in the observed value of blood pressure and pulse rate at each evaluation time point will be calculated.

- For amounts of changes in measured values of blood pressure and pulse rate from values immediately before the start of treatment to each evaluation time point, student's t-test will be conducted using the placebo group as the control.
- Change from baseline in the observed value of blood pressure and pulse rate at each evaluation time point will be divided into categories (blood pressure, < 10 mmHg, ≥ 10 mmHg: pulse rate, < 5 bpm, ≥ 5 bpm), and the frequency of each category will be tabulated.

